### Average Keratinized Mucosa Width

### Statistical Analyses

We used mixed models to analyze the effect of time and treatment on each of the variables of interest. The results are summarized in tables below.

Canfield values, bleeding on probing, plaque index, gingival index, and keratinized mucosa width changed significantly over time. Canfield values, bleeding on probing, plaque index, and keratinized mucosa width have a curved relationship with time. Treatment alone is not significant in any model, but is significant in

an interaction with time in bucco-lingual thickness; the effect of treatment on this measure is significantly different across time points.

Table 13: Canfield Model

	P-Value
Time	< .001
Time 	< .001
Treatment	0.853

Table 14: Probing Depth Model

	P-Value
Time	0.096
Treatment	0.307

Table 15: Bleeding on Probing Model

	P-Value
Time	0.0791
Time 	0.0282
Treatment	0.9170

Table 16: Plaque Index Model

	P-Value
Time	0.1640
Time 	0.0436
Treatment	0.9880

Table 17: Gingival Index Model

	P-Value
Time	0.00146
Treatment	0.40900

Table 18: Bucco-Lingual Thickness Model

	P-Value
Time	0.0744
Time 	0.1440
Treatment	0.6740
Treatment:Time	0.0169
Treatment:Time 	0.0359

Table 19: Keratinized Mucosa Width Model

	P-Value
Time	< .001
Time 	< .001
Treatment	0.106

Over time, there was not a significant relationship between bucco-lingual thickness and any of Canfield values, probing depth, bleeding on probing, or keratinized mucosa.

Table 20: Canfield and Bucco-Lingual Thickness

	P-Value
Time	< .001
Time 	< .001
Thickness	0.178

Table 21: Probing Depth and Bucco-Lingual Thickness

	P-Value
Time	0.0928
Thickness	0.6720

Table 22: Bleeding on Probing and Bucco-Lingual Thickness

	P-Value
Time	0.1190
Time 	0.0381
Thickness	0.7340

Table 23: Keratinized Mucosa Width and Bucco-Lingual Thickness

	P-Value
Time	< .001
Time 	< .001
Thickness	0.705

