### Study objectives

- (Primary) Compare the influence of experimental concavities in the subgingival transition zone of Atlantis™ abutments on peri-implant mucosal dynamics from final restoration delivery to one year, as compared to current Atlantis™ abutments with linear divergent transition profiles.
- (Secondary) Quantify the horizontal soft tissue thickness changes around concave and divergent abutment transition profiles from final restoration delivery to one year.
- (Secondary) Evaluate changes in peri-implant health indicators, such as Gingival Index (GI), Probing Pocket Depth (PPD), and Bleeding on Probing (BOP).

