### Average Plaque Index

### Average Gingival Index

[figure not shown]

Table 11: Bucco-Lingual Thickness

Treatment	Mean	SD	Min	Max	Median	N
Baseline						
Concave	2.814	1.1291	1.0	6.0	2.50	31
Divergent	2.722	1.1294	1.0	6.0	2.50	27
1 Month						
Concave	2.597	0.6248	1.0	4.0	2.50	31
Divergent	2.667	0.6202	1.5	4.0	2.50	27
3 Months						
Concave	2.468	0.5764	1.5	3.5	2.50	31
Divergent	2.840	0.7176	1.5	4.0	3.00	25
6 Months						
Concave	2.517	0.5796	1.5	3.5	2.50	30
Divergent	2.920	0.6403	1.5	4.5	3.00	25
12 Months						
Concave	2.500	0.5000	2.0	4.0	2.50	29
Divergent	2.740	0.7654	1.5	4.0	3.00	25
Average						
Concave	2.594	0.4731	1.9	3.7	2.55	31
Divergent	2.785	0.5159	1.8	3.7	2.80	27

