### Statistical Analyses

We used mixed models to analyze the effect of time and treatment on each of the variables of interest. The results are summarized in tables below.

For Canfield, time was marginally significant but treatment was not. For bucco-lingual thickness, there were significant interactions between treatment and both time and time: the effect of treatment changed over time. In the keratinized mucosa model, neither time nor treatment were significant.

Table 27: Canfield Model (Adjusted for Baseline)

	P-Value
Time	0.0571
Treatment	0.6130

Table 28: Bucco-Lingual Thickness Model (Adjusted for Baseline)

	P-Value
Time	0.5680
Time 	0.5760
Treatment	0.8330
Treatment:Time	0.0465
Treatment:Time 	0.0510

Table 29: Keratinized Mucosa Width Model (Adjusted for Baseline)

	P-Value
Time	0.694
Treatment	0.952

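### For bucco-lingual thickness the Treatment p-value is the arm contrast at delivery, so the report's statement about treatment alone does not test the abutment on that outcome

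*Combined protocol and SAP*

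**What the plan says.** The first Statistical Analyses section of the October 2019 report summarises the mixed models with the statement "Treatment alone is not significant in any model". The remainder of that sentence makes one exception, where it reports significance for "an interaction with time in bucco-lingual thickness; the effect of treatment on this measure is significantly different across time points". The thickness results are in "Table 18: Bucco-Lingual Thickness Model". Its row "Treatment 0.6740" stands with Time 0.0744, Time² 0.1440, Treatment:Time 0.0169 and Treatment:Time² 0.0359. The models in Tables 13 to 17 and 19 print no interaction rows.

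The same structure recurs in "Table 28: Bucco-Lingual Thickness Model (Adjusted for Baseline"), with Treatment at 0.8330. The text above that table comments only on the interactions for thickness. Neither section states how time was coded, and neither gives an estimate, a direction or an interval for thickness.

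The protocol's first secondary objective is to "Quantify the horizontal soft tissue thickness changes around concave and divergent abutment transition profiles" between final restoration delivery and one year. Its Statistical methods section plans arm comparisons of change from baseline at each of the four recalls, with Holm adjustment at an overall 0.05. Quantitative secondary outcomes are to be handled like the primary.

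**The concern.** Once a model contains Treatment:Time and Treatment:Time², the Treatment coefficient is the arm difference where time equals zero. With time counted from delivery, that is the delivery-day difference, before the abutment could act. The report's own Baseline-adjusted Analysis section attributes arm differences at delivery to chance, not to the implant type. In Table 28 the outcome is change from delivery, so the same row extrapolates to a point where the change is zero by construction.

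The summary sentence therefore covers two kinds of row. In the models without interactions, Treatment is an effect across visits. In the thickness model it is a delivery-day contrast. The interaction is disclosed, but a reader cannot learn from the text which arm was thicker after delivery, or by how much. That matters because local thickening of soft tissue is the first mechanism the protocol's background gives for a concave profile, and the recall means point the other way.

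**Working it through.** **1. What the 0.674 refers to.** The time coding is not stated, so I rebuilt the model from printed moments. Means, SDs and Ns come from "Table 11: Bucco-Lingual Thickness". The covariance of delivery with each recall is (SD₀² + SDₜ² − SD_change²)/2, using the SDs of change in Table 25. The correlation among recalls comes from the SD of the Average rows (step 3). Data sets matching these moments were fitted by REML with a random intercept: thickness on treatment × (time + time²).

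| Row | Printed | Rebuilt, months from delivery: median (5th–95th percentile, 60 data sets) |
|---|---|---|
| Time | 0.0744 | 0.077 (0.061–0.091) |
| Time² | 0.1440 | 0.151 (0.128–0.167) |
| Treatment | 0.6740 | 0.704 (0.687–0.717) |
| Treatment:Time | 0.0169 | 0.026 (0.015–0.036) |
| Treatment:Time² | 0.0359 | 0.049 (0.034–0.062) |

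Other codings miss the Treatment row: visit number 0–4 gives about 0.48, visit number 1–5 about 0.13, centred visit number about 0.04 and centred months about 0.014. Months from delivery is the coding that fits.

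One rebuilt fit shows what the row means. Its contrast, divergent minus concave, is −0.07 + 0.159t − 0.011t². At t = 0 this is −0.07 mm (p 0.69). At the mean visit time, (0+1+3+6+12)/5 = 4.4 months, it is −0.07 + 0.700 − 0.213 = +0.42 mm (p 0.014). The model is the same and only the time origin has moved. The second figure lies on the upper part of a fitted curve and is not an overall effect either.

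Table 28 reproduces less closely. One rebuild with months from delivery gave Treatment 0.72 and interactions 0.10 and 0.11, against the printed 0.833, 0.0465 and 0.0510. Visit number 1–4, for which time 0 is again delivery, gave Treatment 0.49. Centred months gave 0.096.

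**2. Differences at each visit.** Divergent minus concave, with SE = s_p√(1/n₁+1/n₂) and s_p the pooled SD. For raw thickness at 6 months, s_p = √[(29×0.5796² + 24×0.6403²)/53] = 0.608. Then SE = 0.608×√(1/30+1/25) = 0.165, t = 0.403/0.165 = 2.45, p = 0.018.

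| Visit | Raw level, Table 11: difference (SE), p | Change from baseline, Table 25: difference (SE), p |
|---|---|---|
| Delivery | −0.092 (0.297), 0.76 | – |
| 1 month | +0.070 (0.164), 0.67 | +0.162 (0.308), 0.60 |
| 3 months | +0.372 (0.173), 0.036 | +0.467 (0.304), 0.13 |
| 6 months | +0.403 (0.165), 0.018 | +0.458 (0.321), 0.16 |
| 12 months | +0.240 (0.174), 0.17 | +0.287 (0.316), 0.37 |

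Holm over four recalls: the smallest raw-level p is 4 × 0.0177 = 0.07; the smallest change p is 4 × 0.130 = 0.52. At 12 months the 95% intervals are −0.11 to 0.59 mm (raw) and −0.35 to 0.92 mm (change).

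**3. Average over the recalls.** (0.070 + 0.372 + 0.403 + 0.240)/4 = +0.271 mm. For its SE, take 25 × SD² of the five-visit average, subtract the five visit variances and twice the delivery covariances, and what is left is twice the sum of the recall covariances:
- Concave: 5.596 − 2.583 − 1.109 = 1.903. Dividing by 2ΣSDᵢSDⱼ = 3.894 gives a correlation of 0.49. Variance of the recall mean: (1.309 + 1.903)/16 = 0.201.
- Divergent: 6.654 − 3.171 − 1.490 = 1.993. Dividing by 5.631 gives 0.35. Variance of the recall mean: (1.895 + 1.993)/16 = 0.243.

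The pooled SD is 0.469. With n 31/27, SE = 0.124, p = 0.032, 95% CI 0.02 to 0.52. With n 29/25, SE = 0.128, p = 0.039, 95% CI 0.01 to 0.53. A common recall correlation of 0.3 gives p 0.021 to 0.026; 0.5 gives 0.042 to 0.050; 0.6 gives 0.054 to 0.064.

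**4. The same question asked in other ways.**
- Recall-averaged contrast from the Table 18 type of model: about 0.27 mm, p about 0.05. The joint test of Treatment and its interactions is also near 0.05.
- Recall mean with delivery thickness as covariate: 0.28 mm, p 0.02 to 0.03.
- Mean change from baseline: (0.162 + 0.467 + 0.458 + 0.287)/4 = 0.34 mm, p about 0.24.
- Five-visit average, Table 11: 2.785 − 2.594 = 0.191 mm, SE 0.130, p 0.147.

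**The case against.** A reader might infer that the report's sentence is false. It is not. Every Treatment row in Tables 13 to 19 exceeds 0.05, and the same sentence names thickness as the outcome where treatment interacts with time. The fault is in letting a delivery-day row stand as a statement about treatment for this outcome, without direction or size.

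A reader might also infer that the report takes 0.833 in Table 28 as an overall null. It does not: the text above that table interprets only the interactions for thickness. The point about Table 28 is that the row needs a label.

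The strongest temptation is to conclude that the concave abutment has been shown to thin the tissue by 0.27 mm. The documents do not support that. The recall average of raw levels is not a planned contrast, its p-value depends on the model and on a derived correlation, and the planned change-from-baseline tests are non-significant at every recall even before Holm. The 12-month difference is non-significant on both scales.

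One reply has weight. Change scores are imprecise here: the delivery SD is 1.13 against 0.50 to 0.77 later, and the implied correlations of delivery with recall are only −0.03 to 0.46. Subtracting baseline therefore mostly adds noise. The change estimates have the same sign as the raw ones, so they do not contradict them. That is a reason to show both, and does not turn a nominal result into a confirmed one.

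In mitigation, thickness is a secondary outcome, all visit means and SDs are printed, and the primary zenith result is unaffected.

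**Conclusion.** The concern holds as a matter of interpretation and reporting. On the evidence of the rebuild, the Treatment row of Table 18 is the arm contrast at delivery and cannot support any statement about treatment alone for thickness. The row in Table 28 has the same defect by its structure, provided time is again counted from delivery; the rebuild supports that coding less firmly there.

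What the row leaves unsaid is that mean thickness was lower in the concave arm at every recall, by 0.07 to 0.40 mm and by about 0.27 mm on average (nominal p about 0.03 to 0.05). Against that stand the non-significant planned change comparisons (p 0.13 to 0.60) and the non-significant 12-month difference.

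The reading of the coding and the visit differences are secure. The p-value for the recall average is not: it assumes equal correlation among recalls within an arm, treats the Average rows as if all visits were present, and passes 0.05 at a common correlation of roughly 0.5 to 0.6. The reporting fault does not depend on which side of 0.05 it falls.

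**What to change.** 1. State the time coding, and note under Tables 18 and 28 that the Treatment row refers to delivery and does not test the abutment.
2. From the fitted models, report the arm contrast at each recall, including 12 months, with 95% intervals and the planned Holm adjustment. Add the joint test of Treatment and its interactions.
3. Report the planned change-from-baseline comparisons for thickness beside them. If a recall-averaged contrast is given, label it post hoc and nominal.
4. Reword the summary sentence so that the statement about treatment alone excludes thickness. For thickness, say that the concave arm had the lower mean at every recall, and in the same place that the planned change-from-baseline comparisons and the 12-month difference were not significant.

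The cost is a few contrast statements on models already fitted and one rewritten sentence. No new data are needed.

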A unified repeated measures analysis (11,12) will be used to describe the time course and to assess the effects of divergent vs. concave abutment design. This approach will make it possible to take into account the correlation of repeated measures on a given subject over time, and to consider the impact of abutment type, as well as other potential covariates. Subject will be treated as a random effect and other factors as fixed effects. Candidate covariate effects that will be explored include sex, age, history of periodontal disease, tooth position, clinical crown anatomy and the condition of adjacent teeth. So as not to exceed the limitations of sample size, we will first consider the relationship of each candidate with the outcome separately, and incorporate those with promising relationships into subsequent modeling. Parameters will be estimated using restricted maximum likelihood

(REML) methods, and a variety of different variance-covariance structures will be entertained, as appropriate. These approaches can accommodate missing data and possible time-dependency of the covariate, both of which may be relevant to this situation. Appropriateness of assumptions associated with the modeling, such as normality, will be fully assessed, and normalizing transformations considered as appropriate. Should these approaches not appear feasible, nonparametric methods for longitudinal data (13, 14) will be considered.

Comparisons of tissue alterations between the two abutments types at each follow-up time are also of interest: Changes relative to baseline will be compared at each of the four recall time points, initially using either the two-sample Student's t-test to compare abutment types, or its nonparametric analog, the Wilcoxon rank sum test, as appropriate. In addition, standard linear modeling will be used to incorporate the possible impact of other covariates. Adjustment for multiple comparisons will be made using the modified Bonferroni method due to Holm (15) in conjunction with an overall Type I error of 0.05.

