Analysis of the quantitative secondary outcomes (e.g., keratinized mucosal widths) will be analogous to that for the primary outcome. In addition, we will also characterize the longitudinal course with respect to the categorical outcomes constituting the clinical periodontal evaluations, with initial emphasis being placed upon transition approaches.(12) These will be considered descriptively in terms of the complete three- or four-point ordinal scales, but specific attention will also be given to shifts from clinically acceptable to clinically unacceptable designations. (16,17)

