#### POWER CONSIDERATIONS:

Evaluations of power and detectable effect size are calculated for change in peri-implant mucosal zenith position at 12-month follow-up relative to baseline over the course of follow-up. Since this research is to be based on a patient population from another study, sample sizes are fixed at 30 subjects for each of the two abutment groups. Assuming dropout of 10-15% over the year of follow-up, calculations were based on completed sample sizes of 27 and 25 per treatment group. Values of 0.4 – 0.7 mm were found in the literature (18, 19) for the standard deviation (s.d.) of this change measure. Taking a conservative approach, estimates of power and detectable effect size were considered for s.d. values of 0.5, 0.7, 0.9 and 1.0 mm; calculations were made based on a Type I error level ( $\alpha$ ) of 0.05 for the key 12-month comparison, as well as  $\alpha = 0.05/4 = 0.0125$ , representing Bonferroni adjustment for four multiple comparisons corresponding to follow-up evaluations at four time points. Due to the scarcity of information in the literature, standard deviation values were assumed to be uniform across time points. Power was set at 80% and 90% for calculations of detectable effect sizes.

A minimum difference of 1 mm between the two abutment groups was felt to be clinically relevant. Based on these sample sizes, at least 99% power is anticipated to detect this effect size, even with adjustment for multiple comparisons and 15% attrition, if the true standard deviation is within the range found in the literature, i.e., 0.7 mm or less. For a larger standard deviation of 1.0 mm, we anticipate 93% power to detect this difference for a single test, and 82% power with multiple comparisons adjustment, again assuming 15% attrition. We therefore anticipate having more than adequate power to detect a clinically important difference in tissue changes between the two abutment designs. The minimum detectable differences are considerably smaller, as indicated in the table below. These results also show that we will be able to detect, with at least 80% power, differences on the order of that considered clinically relevant even if the standard deviation is somewhat greater than that described in the literature cited.

80% POWER								
Sample Size Per Abutment Group+	Detectable Effect Size Between Abutment Groups (mm)							
	Type I Error Level: $\alpha = 0.05$				Type I Error Level: $\alpha = 0.05/4 = 0.0125^*$			
	SD (mm)				SD (mm)			

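### Treatment-by-time terms are shown only for bucco-lingual thickness, one of seven modelled outcomes, and are called significant with no adjustment across outcomes; the result is exploratory

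*Combined protocol and SAP*

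**What the plan says.** The primary objective concerns the influence of the concavity "on peri-implant mucosal dynamics from final restoration delivery to one year". Thickness change is a named secondary objective.

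The protocol's Statistical methods section plans a repeated measures model for the time course and the abutment effect. It names no treatment-by-time test and no rule for keeping or dropping one. For the comparisons of change at the four recall visits it promises adjustment "using the modified Bonferroni method due to Holm (15) in conjunction with an overall Type I error of 0.05". Quantitative secondary outcomes are to have an analysis that "will be analogous to that for the primary outcome". The power section counts the same family, "representing Bonferroni adjustment for four multiple comparisons corresponding to follow-up evaluations at four time points". Neither section counts outcomes.

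In the report's first Statistical Analyses section:
- Tables 13-17 and 19 (Canfield, probing depth, bleeding, plaque index, gingival index, keratinized mucosa width) show time, sometimes time², and treatment.
- Only Table 18 (thickness) adds Treatment:Time (0.0169) and Treatment:Time² (0.0359).
- The text finds no treatment main effect in any model and then says of thickness that "the effect of treatment on this measure is significantly different across time points".

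In the baseline-adjusted section, Tables 27 and 29 show no interaction rows. Table 28 (thickness) shows 0.0465 and 0.0510, and the text describes the interactions with both time terms as significant. No multiplicity adjustment is mentioned in either section.

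**The concern.** The thickness interaction is the only treatment-related result the report presents as significant. It is judged at its nominal p-value, with six other outcomes modelled beside it and no interaction result given for any of them. Either further interaction tests were run and not shown, or one secondary outcome was modelled differently from the rest without a stated reason. The second would sit badly with the commitment to analogous analyses.

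The primary outcome is among the six. Table 13 includes the delivery visit, so its treatment row without an interaction compares average level between arms. Whether the arms diverge over time is the treatment-by-time question, and it is not reported for Canfield. At stake is whether a reader takes the thickness finding as established or as a lead to be confirmed.

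**Working it through.** **Plan's own figure.** The power section says "calculations were based on completed sample sizes of 27 and 25 per treatment group". For n = 25 per arm, a 1 mm difference and SD 1.0 mm, the noncentrality is 1/(1.0 × √(2/25)) = 3.54 on 48 df. Two-sided t-test power is 93.4% at α = 0.05 and 82.2% at 0.0125, against the stated 93% and 82%. So the plan's multiplicity allowance is for four visits (0.05/4) and nothing else.

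**Error rate across outcomes, if all seven interactions were examined at 0.05.**
- One test each, independent: 1 − 0.95^7 = 0.302.
- Either of two polynomial terms may count: simulation under no effect, with visits at 0, 1, 3, 6 and 12 months, gives 6.2% per outcome, so 1 − 0.938^7 = 0.36. If two terms count only in the five models that carry time² (Tables 13, 15, 16, 18, 19), it is 35%.
- Equal correlation between outcomes of 0.5 (assumed; the documents give none): 23% with one term, 28% with either.

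**Holm**, taking the shown p-value as the smallest in its family:
- Table 18, six secondary outcomes: 6 × 0.0169 = 0.101.
- Table 18, all seven: 7 × 0.0169 = 0.118.
- Table 28, three baseline-adjusted outcomes: 3 × 0.0465 = 0.14.

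**Joint two-term test for thickness.** Each Table 18 p-value is for a single coefficient, so I rebuilt the joint test.
- Divergent minus concave means in Table 11 at months 0, 1, 3, 6, 12: −0.092, 0.070, 0.372, 0.403, 0.240.
- Quadratic fit: linear 0.151, quadratic −0.0105. The matching elements of (X'X)⁻¹ are 0.1526 and 0.000955, covariance −0.01164.
- Average N from Table 11: 152/5 = 30.4 and 129/5 = 25.8, so 1/30.4 + 1/25.8 = 0.0717.
- Residual SD is not stated; 0.60 is assumed. Linear z = 0.151/(0.60 × √(0.1526 × 0.0717)) = 2.41, p = 0.016. Quadratic z = −2.12, p = 0.034. These are close to Table 18, which supports the assumed SD.
- Wald statistic 6.36 on 2 df: p = exp(−6.36/2) = 0.04. It scales with 1/SD², so SD 0.55 gives 7.57 (p = 0.02) and SD 0.65 gives 5.42 (p = 0.07).
- Times six: about 0.25 at SD 0.60, and 0.14 to 0.40 over the range.

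**Planned visit comparisons for thickness**, two-sample t-tests on the Table 25 changes. At 3 months the difference is 0.120 − (−0.347) = 0.467. The pooled variance is (30 × 1.030² + 24 × 1.244²)/54 = 1.277, the SE is √(1.277 × (1/31 + 1/25)) = 0.304, t = 1.54 and p = 0.13. The four visits give p = 0.60, 0.13, 0.16 and 0.37. None is below 0.05 even before Holm.

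**Canfield slope difference from Table 24.**
- Concave minus divergent at 1, 3, 6, 12 months: 0.024, 0.025, 0.036, 0.064. Month values centred at 5.5 have sum of squares 69, so the slope is 0.2635/69 = 0.0038 mm/month.
- With an assumed residual SD of 0.12, SE = 0.12/√69 × √(1/29 + 1/25) = 0.0039, z = 0.97 and p = 0.33. For SD 0.10 to 0.15, p is 0.25 to 0.44.
- Support for 0.12: the pooled slope in Table 24 is −0.00369, and the Time p-value of 0.0571 in Table 27 means |z| = 1.90. The implied SD is 0.00369/1.90 × √(69 × 54) = 0.118.

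**The case against.** The strongest reply is that selection is not documented. A reader might infer that interactions were fitted in all seven models and only the significant one kept, and so that a third of null trials would produce such a finding. The report's wording suggests this but does not say it. If the interaction was fitted only for thickness, neither the 30-36% nor the multipliers describe what was done. Independence is also doubtful, because plaque index, gingival index, probing depth and bleeding come from the same six sites in the same subjects. Both points stand, so the rates are conditional and carry a range.

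It can also be said that dropping null interactions is common, that thickness was a named secondary objective, that control across secondary outcomes was never promised, and that Table 27 does compare Canfield change averaged over follow-up (treatment p = 0.6130). All outcomes are tabulated by arm and visit. Nor is a benefit being inflated: Table 11 shows the concave arm thinner from month 1, against the thickening rationale in the protocol's background.

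These points limit the consequence but do not justify an unqualified claim of significance. No hierarchy or interaction test was set for thickness, and whatever one thinks of formal control across secondary outcomes, an unplanned interaction shown for one outcome is exploratory. None of them explains calling 0.0510 significant.

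**Conclusion.** The thickness interaction is overstated. It is nominally below 0.05 in Table 18, but 0.0169 becomes 0.10 under Holm over six secondary outcomes (0.118 over seven), and 0.0465 becomes 0.14 over the three baseline-adjusted outcomes. These figures assume the shown p-value is the smallest in its family; they do not depend on the correlation between outcomes. The rebuilt joint test, which rests on an assumed residual SD, is borderline before adjustment and fails after it. The planned visit comparisons show nothing.

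The false-positive rate (about 30%, up to about 36%, or 23-28% at correlation 0.5) holds only if all seven interactions were examined. The documents do not support a firm statement that results were selected, nor a suspicion that a primary signal is hidden: the rebuilt Canfield p is about 0.33. The primary conclusion is unaffected. This is a correction that should be made to reporting and labelling.

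**What to change.** - State whether treatment-by-time terms were fitted for the other outcomes and, if so, the rule for dropping them.
- Report one joint treatment-by-time test for every outcome, Canfield first as the primary. Give nominal and Holm-adjusted p-values across the six secondary outcomes.
- Reword the thickness statements in both Statistical Analyses sections as exploratory findings, with both p-values beside them.
- Stop describing the 0.0510 in Table 28 as significant.

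The cost is a few further tests from models already set up and some reworded sentences. The downside is that the thickness result becomes exploratory.

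### Table 18's thickness p-values fit a single residual variance that Table 11 contradicts, and the treatment-by-time claim drawn from them lacks the joint two-degree-of-freedom test it needs

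*Combined protocol and SAP*

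**What the plan says.** The protocol (Statistical methods) plans a REML repeated-measures model with subject as a random effect. On the covariance it says that "a variety of different variance-covariance structures will be entertained, as appropriate"; no structure is fixed.

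The statistical report of October 1, 2019 (Statistical Analyses) says only: "We used mixed models to analyze the effect of time and treatment on each of the variables of interest". "Table 18: Bucco-Lingual Thickness Model" lists p-values without estimates, standard errors or a residual structure: Time 0.0744, Time² 0.1440, Treatment 0.6740, Treatment:Time 0.0169, Treatment:Time² 0.0359. From the last two, the text concludes that the effect of treatment on thickness differs significantly between visits. It reports no other significant treatment effect before baseline adjustment.

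"Table 11: Bucco-Lingual Thickness" prints mean, SD, minimum, maximum, median and N. The delivery rows are "Concave 2.814 1.1291 1.0 6.0 2.50 31" and "Divergent 2.722 1.1294 1.0 6.0 2.50 27". The smallest and largest recall SDs are both at 12 months: "Concave 2.500 0.5000 2.0 4.0 2.50 29" and "Divergent 2.740 0.7654 1.5 4.0 3.00 25".

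**The concern.** Delivery readings range from 1 to 6 mm, and recall readings from 1 to 4.5 mm. A model with one residual variance gives the delivery reading the same weight as a recall reading. With time and time² in the model, delivery anchors the start of each arm's curve. Two things are at stake: whether the standard errors behind the interaction p-values are valid for the estimates they accompany, and whether two single-coefficient p-values can support a statement about the whole time course.

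**Working it through.** **1. Variance ratios (Table 11).** Ratio = delivery SD² / recall SD².
- Concave at 12 months: 1.1291² / 0.5000² = 1.275 / 0.250 = 5.10. All four recalls: 3.27, 3.84, 3.79, 5.10.
- Divergent at 12 months: 1.1294² / 0.7654² = 1.276 / 0.586 = 2.18. All four recalls: 3.32, 2.48, 3.11, 2.18.

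The range is 2.2–5.1 for variances, or 1.5–2.3 for SDs.

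**2. Is this more than chance?** The delivery–recall covariance follows from the change SDs in Table 25: C = (V₀ + Vₜ − V_change)/2. The paired Pitman–Morgan test uses r = (V₀ − Vₜ)/√[(V₀ + Vₜ + 2C)(V₀ + Vₜ − 2C)].
- Weakest case, divergent at 12 months: C = (1.276 + 0.586 − 1.036²)/2 = 0.394. Then r = 0.690/√(2.649 × 1.073) = 0.409, and with n = 25, t = 2.15 and p = 0.042.
- Strongest case, concave at 12 months: r = 0.672, n = 29, p = 0.00006.

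All eight comparisons fall below 0.05.

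**3. Which model fits Table 18?** Exact reproduction needs patient data. The covariance matrix of each arm was rebuilt from the Table 11 SDs, the covariances in step 2, and the SD of the subject averages, which gives the mean correlation among recalls. For concave: 25 × 0.4731² = 5.596; less the variances (2.583) and twice the delivery covariances (1.108), then halved, this leaves 0.952. Divided by the sum of SD products (1.947), that is a correlation of about 0.49. For divergent it is about 0.35.

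Twenty-five data sets with these moments, equal recall correlations and dropout to the printed Ns were fitted by REML, with months 0, 1, 3, 6 and 12. Median p (10th–90th percentile):

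| Term | Table 18 | One residual variance | Separate delivery variance |
|---|---|---|---|
| Time | 0.0744 | 0.084 (0.069–0.100) | 0.248 (0.190–0.285) |
| Time² | 0.1440 | 0.164 (0.134–0.196) | 0.335 (0.264–0.397) |
| Treatment | 0.6740 | 0.714 (0.668–0.739) | 0.851 (0.762–0.889) |
| Treatment:Time | 0.0169 | 0.025 (0.018–0.047) | 0.027 (0.018–0.046) |
| Treatment:Time² | 0.0359 | 0.053 (0.033–0.093) | 0.043 (0.024–0.077) |

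The first three rows fit one variance and not two; the interaction rows do not discriminate. The extra delivery variance lowers −2 log-likelihood by 136.5 − 82.9, about 54, for one parameter. A decaying recall correlation gives nearly the same results.

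**4. Standard errors of the one-variance estimates.** For Treatment:Time the model-based SE is 0.067, and the sandwich SE is 0.077–0.078. The ratio is about 1.15. For Treatment:Time² the ratio is about 1.05–1.08. The true level of a nominal 5% test is 2[1 − Φ(1.96/ratio)]: 8.7% at 1.145 and 6.2% at 1.052.

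**5. Weight of the delivery reading.** Taking concave as the reference arm, the linear Time coefficient is about −0.080 mm/month with one variance and about −0.050 with a separate delivery variance.

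**6. Interactions with unequal variances.** Treatment:Time moves from about 0.153 (SE 0.067) to 0.140 (SE 0.063). Single-term p-values are about 0.023–0.028 and 0.034–0.043 across separate-delivery, visit-specific and unstructured forms.

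**7. Joint test of both interaction terms (2 df).** The rebuilt p is about 0.06 with equal variances (0.044–0.071 over variants of the rebuild) and about 0.07–0.09 with unequal variances. A further run of 15 data sets gave somewhat lower medians for the unequal-variance forms, 0.058–0.072, depending on the form and on whether the denominator df was 50 or 219.

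**The case against.** The strongest objection is that the recommended refit does not weaken the reported terms. Their SEs fall slightly and both stay below 0.05. This stands. A reader might infer that the interactions are significant only because equal variances were assumed; step 6 does not support that. Nor should sandwich p-values from the rebuild be set against Table 18, because the rebuild's uncorrected p-values are already higher than the reported ones. Rescaling the reported values instead gives z = 2.389/1.145, p = 0.037, for the linear term. For the quadratic term, z = 2.098/1.052 gives p = 0.046, or 0.052 at a ratio of 1.08.

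Second, the structure is inferred, not stated. This also stands: one variance is the better match but is not proven.

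Third, the joint result owes more to the choice of test than to the variances, and the protocol does not specify a joint test. That is correct. The test is nevertheless the one that the report's sentence requires. The linear and quadratic coefficients describe a single curve, and neither p-value alone says whether the arms differ over time.

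Fourth, the report prints no slope and does not list thickness among the outcomes that changed over time, so the slope difference in step 5 contradicts no published claim. It shows only how much the delivery reading influences the fit. Nor is the protocol breached, since it left the structure open.

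Finally, Table 28, where delivery is no longer an outcome row, already shows borderline values (0.0465 and 0.0510). That supports cautious wording; yet the accompanying text calls both interactions significant.

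**Conclusion.** The concern holds in a limited form. Unequal variance is established from the report's own SDs. The inference that Table 18 used one residual variance is well supported but indirect. If it did, the SE of its Treatment:Time estimate is too small by about 15% and that of Treatment:Time² by about 5–8%, and delivery is over-weighted.

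Allowing for the variances leaves both single-term interactions below 0.05. The statement about differences across visits is a joint claim, and its rebuilt p lies a little above 0.05: about 0.06 with equal variances in most variants, and about 0.07–0.09 with visit-specific ones. The evidence is better called borderline, subject to a refit on the patient data.

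The size of these effects rests on assumed recall correlations, monotone dropout and months as the time scale. Thickness is a secondary outcome, and the primary zenith analyses (Tables 13 and 27) are not affected. The point matters because this is the report's only positive treatment claim.

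**What to change.** Refit Table 18 with visit-specific residual variances, or an unstructured covariance, and small-sample degrees of freedom such as Kenward–Roger or Satterthwaite. State the structure chosen, and print estimates and SEs beside the p-values. Report the joint 2-df treatment-by-time test and base the sentence in Statistical Analyses on it, calling the evidence borderline if the test does not reach 0.05.

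The cost is a refit of one model on existing data. The downside is up to four more variance parameters and probably a less favourable headline p-value.
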